4. SPECIFIC AIMS/HYPOTHESES

Aim 1: Confirm that Kidpower-Structured Games engages neural and behavioral markers of EC. We hypothesize that Kidpower-Structured Games will produce greater increases in neurophysiological and behavioral markers of EC than Kidpower-Child-Led Play (CLP, active comparator).

Aim2: Assess the relationship between pre- to post-Kidpower-Structured Games change in neurobehavioral markers of EC and change in clinically significant anxiety. We hypothesize that increases in neurophysiological and behavioral measures of EC will relate to reductions in clinically significant anxiety from pre-to-post Kidpower- Structured Games. Exploratory analyses will examine the moderating effects of baseline threat reactivity on the relation between pre- to post-treatment increase in EC and reduction in anxiety severity.

Aim 3: Explore dosing effects of Kidpower-Structured Games on behavioral EC targets and anxiety symptoms. We hypothesize that greater at-home practice of Kidpower-Structured Games exercises will relate to greater engagement of neural and behavioral markers of EC targets and greater reduction in anxiety symptoms. Dosage will be assessed by weekly parent report on child practice of EC exercises at home (frequency, duration).

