5. BACKGROUND AND SIGNIFICANCE

Preschool anxiety is prevalent, with 20% of children affected (Bufferd et al, 2012). Among these, a majority will continue to experience symptoms throughout adolescence and adulthood (Bittner et al, 2007). Early childhood anxiety also predisposes to a host of negative, long-term outcomes, including major depression and substance abuse (Bittner et al, 2007; Zimmerman et al, 2003), underscoring the importance of early intervention.

We will test a neuroscientifically-derived intervention targeting effortful control (EC) skills, low levels of which have been linked to greater emotional reactivity and clinical anxiety. Defined as the ability to effectively regulate behavior and emotion, EC reflects the activity of frontal brain systems and can be indexed by an event-related brain potential, the error-related negativity (ERN) and time frequency interchannel phase synchrony (ICPS) (Moran et al, 2015). The ERN is a neurophysiological response, localized to the dorsal anterior cingulate cortex, signaling the need for adaptive behavioral adjustments following errors (Gehring et al, 2018). The ICPS reflects the transmission of this error signal to the dorsolateral prefrontal cortex in order to implement the specified control (Cavanagh et al, 2009).

Findings from our labs and the work of others have shown that reduced ERN and ICPS relate to behavioral deficits in EC and enhanced threat reactivity (Lo et al, 2015) similar to that documented in clinically anxious children (Meyer, 2017). In response, our team developed a child-friendly group EC training, Camp Kidpower-Structured Games, designed to increase ERN, ICPS and related EC behaviors in the service of decreasing anxiety symptoms in preschoolers. Results of our pilot study indicate that this brief EC training approach engaged the intended EC neural and behavioral targets and reduced anxiety symptoms (Schroder et al, 2022). Building on this pilot work, the current project aims to replicate and extend these findings in a larger sample using a randomized controlled design.

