The Kidpower-Structured Games condition will be tested against an active comparator "Child-led Play" condition (Kidpower-CLP). Kidpower-Structured Games will involve executive function training games, shown to improve executive function skills in preschoolers (Diamond and Ling, 2016) and tested previously for the treatment of children with ADHD (Halperin et al, 2013). Kidpower-CLP will permit identification of specific effects of the EC training by controlling for confounds including: a) participation in a fun playgroup; b) interaction with new children during activities; c) separation from parents; and d) time spent with new adults. As detailed next, Kidpower-CLP is derived from evidence based treatment for early childhood psychopathology; in this study, it will include structured play activities (art activities, dramatic play, and story time), but not EC games. Both Kidpower-Structured Games and -CLP conditions will be delivered to small groups of clinically anxious preschoolers by study team members at the same staff to child ratio.

Child-led play has been shown to foster the development of cognitive, physical, social, and emotional well-being of children (Ginsburg et al, 2007). Moreover, play is important to healthy brain development (Shonkoff and Phillips, 2000; Frost, 1998; Tamis-Lemonda et al, 2004). When play is allowed to be child driven, children practice decision-making skills, move at their own pace, discover their own areas of interest. Additionally, child-led play promotes healthy parent-child attachment. The most widely employed early childhood psychotherapy, Parent Child Interaction Therapy (PCIT), focuses on Child-led Play for the first half of treatment. During this portion of PCIT, children experience child-directed play with their parents to encourage warm, secure caregiver-child relationships (Lieneman et al, 2017). The child-led play condition in Camp Kidpower gives children the opportunity to direct their own play at camp, while training parents to deliver child-led play at-home. As such, it fosters development across cognitive, social, neural and relational domains.

6. RESEARCH DESIGN AND METHODS (1 page maximum)

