Participants are randomized to a camp-style intervention ("Camp Kidpower"), which includes either EC training (Kidpower-Structured Games) or child-led playgroup (active comparator; Kidpower-CLP). Before and after the 4-week intervention, a multi-level assessment will be completed, including clinical interview with parent about their child's anxiety symptoms, parent-report surveys on child and self, lab-observed behavioral tasks and electroencephalogram (EEG) with child. Primary analyses will test for group mean differences in neurophysiological and behavioral indices of EC from time 1 (pre-intervention) to time 2 (post-intervention) among children assigned to Kidpower- Structured Games training compared to those assigned to Kidpower-CLP. Secondary analyses will test relationship of changes in neurophysiological targets with change in EC behaviors and change in anxiety severity.

The Kidpower-Structured Games were adapted from a group-based intervention originally designed to treat EC deficits in children with attention deficit hyperactivity disorder (Halperin et al, 2013) and a recently published review of executive function and effortful control interventions (Diamond and Ling, 2016). Kidpower-CLP was developed by the study team to include all of the same elements as Kidpower-Structured Games except for EC training games.

Both Kidpower-Structured Games and Kidpower-CLP will occur over 4-5 sessions, for approximately 3 hours each session. Sessions may be delivered back-to-back or over the course of four weeks. Times will be chosen to maximize child focus and energy and to provide the most convenience for families. Regardless of condition, children will begin with a group welcome activity, then will complete 1-2 of the intervention exercises for that day with their camp counselor. After a brief break and snack, children will complete the remaining 1-2 intervention exercises with their camp counselor, then come back together for a final group activity. The last 30 minutes of camp will include parents, who will be assigned daily homework involving the same play as at camp to complete with their child in between camp sessions. Two parent meetings (led by the lead camp counselor) will take place; the first will occur prior to the beginning of camp to orient parents, and the second will be held mid-way through camp to answer questions that may have arisen.

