Error-eliciting Zoo Task: The "Zoo task", a "Go/No-Go" paradigm assessing effortful control, has been found to reliably elicit ERN in preschoolers (Grammer et al, 2014). Before performing the task, children are instructed to help the game's zookeeper find all the escaped animals. Children then view a series of animals on a computer screen and are asked to press a button when a new animal appears (Go trials), unless the animal is an orangutan (i.e., inhibit button response,

No-Go trials). The task includes 8 blocks, each containing 30 unique animals (Go trials) and 10 orangutans (No-Go trials) in random order.

Error Related Negativity (ERN): As children play the Zoo task, EEG data will be recorded from 32 scalp sensors embedded in an elastic cap using the BioSemi Active 2 system (Amsterdam, The Netherlands). ERPs from fronto-central recording sites time-locked (within 100 ms) to error and correct response will be examined. Differentiation between these trial types is the primary ERN measure, but we will also consider ERN on error trials, as well as ERPs on correct trials separately. Previous research indicates that the ERN demonstrates good psychometric properties across children, adolescents and adults. The number of NoGo errors and response times (RTs) to Go trials will also be considered in NP analyses, as performance can affect ERN amplitude.

Time Frequency Interchannel Phase Synchrony (ICPS): Using the same approach previously employed by our group, complex time-varying energy time-frequency distributions (TFDs) of all the EEG signals at each channel extracted from the Zoo task (described above) will be obtained using the reduced interference distribution (RID) Rihaczek distribution. RID based TFDs offer improved time-frequency support relative to wavelets. Functional connectivity will be assessed using interchannel phase synchrony (ICPS), based on the phase locking value (PLV), derived from the RID TFDs. Current source density (CSD) transform will be applied to EEG data before phase synchrony analysis to reduce volume conduction, using published methods. We will focus on ICPS within the theta band in the ERN time window. Consistent with previous work, the current study will report ICPS between FCz and lateral frontal sites, indexing mediolateral functional connectivity, indexing control processing.

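### Does Aim 1 need a multiplicity rule because several effortful-control indices are jointly primary?

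*Combined protocol and SAP*

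**What the plan says.** Section 4 states Aim 1 as "Confirm that Kidpower-Structured Games engages neural and behavioral markers of EC", with the directional hypothesis that Structured Games "will produce greater increases in neurophysiological and behavioral markers of EC than Kidpower-Child-Led Play". Section 6 carries this into the analysis: "Primary analyses will test for group mean differences in neurophysiological and behavioral indices of EC", comparing change from before to after the intervention between the two arms.

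The targets are named in Section 5, which describes the training as "designed to increase ERN, ICPS and related EC behaviors in the service of decreasing anxiety symptoms in preschoolers". That gives three: ERN, ICPS and EC behavior.

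Section 6 then fixes part of the detail.

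- **ERN:** "Differentiation between these trial types is the primary ERN measure, but we will also consider ERN on error trials". The contrast is fixed. The fronto-central sites are plural and unnamed.
- **ICPS:** "We will focus on ICPS within the theta band in the ERN time window", and "the current study will report ICPS between FCz and lateral frontal sites". Band, window and the midline site are fixed. The lateral sites, and whether they are averaged, are not.
- **Behavior:** the source batteries are given as examples and no single EC score is named. A list of measures and their timing is said to be in the Uploads section, which was not available here.

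Section 7 describes the purpose as examining mechanistic plausibility and gives the sample: 71 and 43 children from two other datasets plus up to 20 new ones. The supplied text contains no alpha, sidedness, multiplicity adjustment, ranking of indices or success rule.

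**The concern.** Aim 1 uses confirmatory language and several indices share primary status. If each is tested at the usual level and any one positive result is reported as target engagement, the chance of a false claim is two to three times that of a single test. Target engagement is the trial's main claim, so its error rate would rest on a rule that nobody wrote down.

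The open details (ERN sites, ICPS pairs, behavioral score) add room to choose among versions of each index after the data are seen. Most of the pooled data come from the two other datasets, which makes the timing of such choices matter more.

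**Working it through.** The documents give no alpha, power or sample-size calculation, so there is no figure of the plan's own to reproduce. The check asks how the false-claim rate depends on the unstated success rule, and what the proposed remedy would cost.

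**Inputs.** From the documents: three targets (Section 5), a directional hypothesis (Section 4), and a pooled maximum of 71 + 43 + 20 = 134 children (Section 7). Assumed, because the documents do not give them: two-sided 0.05 per test (cut-off c = 1.96), equal correlation r from 0 to 0.7 between test statistics, a standardized difference of 0.5, 1:1 allocation, and 100 analyzable children as an example of EEG loss.

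**False claims favoring Structured Games, no true effect on any index.** A single test gives 0.025. Given a shared normal factor u, each index passes with probability p(u) = 1 − Φ((c − √r·u)/√(1−r)). Each rule below is averaged over u.

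| Success rule | Expression | r = 0 | r = 0.5 | r = 0.7 |
|---|---|---|---|---|
| Any one of three | 1 − (1 − p)³ | 7.3% | 6.3% | 5.5% |
| Behavior plus at least one neural | p·[1 − (1 − p)²] | 0.12% | 0.76% | 1.2% |
| All three | p³ | 0.002% | 0.16% | 0.44% |
| Holm over three, any one | simulation | 2.5% | 2.2% | 1.9% |

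By hand at r = 0: any one is 1 − 0.975³ = 0.0731; behavior plus one neural is 0.025 × (1 − 0.975²) = 0.0012; all three is 0.025³ = 0.000016. Counting false findings in either direction, the any-one figures are 14.3% (r = 0) to 10.9% (r = 0.7), against 5% for one test.

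The any-one result also moves with the number of indices. Over r = 0.7 to 0 it is 4.2% to 4.9% for two and 7.4% to 11.9% for five.

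**Power per index.** The expected z is 0.5 × √(N/4), which is 2.894 at N = 134 and 2.5 at N = 100.

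- Unadjusted: Φ(2.894 − 1.96) = 82% at N = 134, and Φ(2.5 − 1.96) = 71% at N = 100.
- Holm, all three indices truly different: 77% to 78% and 62% to 63% (r = 0.5 to 0).
- Holm, only one truly different: about 69% and 54%. The losses are 82.5 − 69.3 = 13 points and 70.5 − 54.4 = 16 points.

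**Power of the behavior-plus-one-neural rule, unadjusted, all three truly different.** At r = 0 and N = 134 this is 0.825 × (1 − 0.175²) = 0.80. Over r = 0 to 0.7 it is 79% to 80%. At N = 100 it is 64% to 66%.

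Section 5 says both conditions "will be delivered to small groups of clinically anxious preschoolers by study team members". Any clustering by group would lower all these power figures further.

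**The case for a change.** The strongest case for a change is that the dependence is itself the defect. A false-claim rate anywhere from near zero to 7.3%, according to a rule the plan omits, is poor form for an aim that sets out to confirm something. A list of measures in the Uploads section would not by itself supply an alpha or a decision rule. One sentence would settle the point, and it is most credible if written before any comparison by arm.

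Much of this stands. The rule is missing, and the arithmetic for the any-one reading is right. Nor is the conjunctive reading fully protective: its 0.1% to 1.2% assumes no effect on any index. If behavior truly changed and neither neural index did, a claim covering both domains would rest on either of two neural tests and could be false up to 4.2% to 4.9% of the time.

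What does not follow is a particular change. Holm with separate claims would let Aim 1 be declared on ERN alone, although the aim names neural and behavioral markers together. If both domains were meant to be needed, that would loosen the rate with no true effects from at most 1.2% to between 1.9% and 2.5%. Naming one score per index would still leave the ERN sites, the ICPS pairs and the behavioral score to the sponsor, and the supplied text offers no basis for choosing them.

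**Conclusion.** No change to the plan follows. This is a rule left unwritten, not a stated rule that gives a wrong answer. The headline inflation, 5.5% to 7.3% against 2.5%, belongs to one reading only. Reading the word joining neural and behavioral markers in Sections 4 and 6 as a requirement for both domains brings the rate under no true effect to between 0.1% and 1.2%, below the single-test level.

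Analysts can fill the gap sensibly from what is there. Three targets are named, the ERN contrast is labeled primary, and the ICPS band, window and midline site are set. Reporting all three results side by side lets a reader judge whether engagement was shown in one domain or both.

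The choice between Holm and a both-domains rule is a fair trade-off in a study of mechanistic plausibility. Holm gives a guarantee for each index but loses 13 to 16 points of power when only one index truly differs. The both-domains rule has about 79% to 80% power at 134 children if all three differ, without an adjustment. All these figures rest on the assumed alpha, count of three, correlation of 0 to 0.7, difference of 0.5 and equal allocation without clustering, none of which the documents state.

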Behavioral Measures: Pre/post behavioral tasks are drawn from widely employed temperament protocols - e.g., Lab-TAB, Kochanska battery (Kochanska et al, 1996), and the age-normed NIH Toolbox (Zelazo et al, 2013). In addition to these tasks, free play time will be given to children and parent during the session. Behavioral tasks will be videotaped (if consent is given) for analysis. Behavioral tasks total approximately 2 hours per visit.

While completing select behavioral tasks (potential threat task, speech task, and bubbles task) (McGinnis et al, 2016), children may be asked to wear a lab-owned smartphone attached to a belt that will be worn around the child's waist. The smartphone uses a custom program, designed specifically for this research application/data collection and is not publicly available. It will guide administrators through the tasks by prompting them to press a 'start' and 'stop' button for data collection. It stores raw motion and audio data from the smartphone's accelerometer and microphone, labeled only with a de-identified numeric ID. The smartphone will not be connected to either cellular or wireless networks during data collection. This de-identified data will be transferred to the secure servers via physical wire and immediately deleted from the device after each lab visit. Motion and audio data on tasks are especially helpful for generating behavioral indices of fear. In the potential threat task, children walk besides experimenter towards a covered terrarium, and motion data indexes reluctance to approach-- a behavioral correlate of Fear. In the speech task, audio data can be submitted to machine learning algorithms to discern speech patterns associated with anxiety severity. Motion and audio data during the Bubbles task will be used to generate a behavioral index of Reward.

Clinical Measures: May include a combination of clinician-assessed and clinical self-report measures for child anxiety and depression, temperament, development, intelligence, and parent psychopathology and experiences. These may be administered during screening, at either of the lab visits, and/or during the follow-up phone call. Questionnaires may be administered via paper forms or via online via a secure application such as Qualtrics. A summary of measures and timing for administration is included in the Uploads section.

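### Does allowing back-to-back camps undermine the pre-to-post comparison or the Aim 3 home-practice analysis?

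*Combined protocol and SAP*

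**What the plan says.** Section 6 of the combined protocol and SAP places the assessments around a camp of fixed length: "Before and after the 4-week intervention, a multi-level assessment will be completed". The primary comparison uses those two time points: "Primary analyses will test for group mean differences in neurophysiological and behavioral indices of EC from time 1 (pre-intervention) to time 2 (post-intervention". Later in the same section, the number and length of sessions are set for both arms together: "Both Kidpower-Structured Games and Kidpower-CLP will occur over 4-5 sessions, for approximately 3 hours each session". The next sentence gives the choice of schedule: "Sessions may be delivered back-to-back or over the course of four weeks". Parents "will be assigned daily homework involving the same play as at camp to complete with their child in between camp sessions".

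Section 4 states Aim 3 as an exploratory question: "Explore dosing effects of Kidpower-Structured Games on behavioral EC targets and anxiety symptoms". It defines the exposure as follows: "Dosage will be assessed by weekly parent report on child practice of EC exercises at home (frequency, duration". Section 6 refers the reader elsewhere for the calendar of measurements: "A summary of measures and timing for administration is included in the Uploads section". That summary is not part of the text available for review.

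**The concern.** Four weeks is the length of the camp in one sentence and one of two options in another, and both cannot describe every camp. The difference seems to matter in two places.

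First, camp length makes up part of the interval between time 1 and time 2 in the primary analysis, and the text gives no visit window that would fix that interval in another way.

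Second, the Aim 3 dose is collected weekly and homework falls between sessions. A camp completed within a few days leaves little time to practise and about one report to record it. Dose would then depend partly on the schedule and not only on the family's effort. If schedule also influenced outcome directly, a slope of outcome on dose that ignored schedule could be misleading.

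**Working it through.** The plan gives no figure of its own on this point, so the check is a count followed by reasoning about each analysis.

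**Inputs from the documents.** 4 to 5 sessions of about 3 hours; back-to-back delivery or delivery over four weeks; homework between sessions; weekly parent report. **Assumption.** Back-to-back means one session a day on consecutive days.

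**Contact time.** 4 × 3 = 12 hours to 5 × 3 = 15 hours under either schedule. The schedule does not change it.

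**Days from first to last session.**
- Consecutive days: 4 − 1 = 3 days, or 5 − 1 = 4 days.
- Spread: four weekly sessions take 3 × 7 = 21 days; the full 28-day span is 28 − 1 = 27 days.
- Ratios at equal session count: four sessions, 21/3 = 7 to 27/3 = 9; five sessions over the full span, 27/4 = 6.75.

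**Weekly reports.** 3 to 4 days fall within one 7-day period, so there is about one report. For a spread camp, 21/7 = 3 and 27/7 = 3.9, so three to four. If a weekend interrupts a back-to-back camp, it still covers only about a week.

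**Dose metric.** Section 4 does not say whether dose is a total or a frequency per week. On the per-week reading the gap is much smaller: at most 3 or 4 practice days against 7, so 7/4 = 1.75 to 7/3 = 2.33.

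**Aim 1.** The comparison is between randomized arms, and the schedule option is written for both. A shorter or longer interval that is balanced across arms affects both mean changes and does not bias their difference.

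**Aim 3.** Confounding by schedule needs two things together: both formats in the data, and an effect of format on outcome that does not pass through practice. If no camp ran back-to-back, format cannot confound. If format acts only through practice, the variation it creates is real dose variation.

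**Cost of adjusting the Aim 3 slope for format.** Let q be the back-to-back share, A and B the days available in spread and back-to-back camps, and m and s the mean and SD of the fraction of days practised. Then

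share of dose variance due to format = q(1−q)[m(A−B)]² / {q(1−q)[m(A−B)]² + s²[qB² + (1−q)A²]}

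and the standard error grows by 1/√(1 − share). Assume m = 0.6 and s = 0.25; the documents give neither.
- Total dose, A/B = 21/3, q = 0.10: 10.50/(10.50 + 24.86) = 0.30, factor 1.19.
- Total dose, A/B = 21/3, q = 0.50: 29.16/(29.16 + 14.06) = 0.67, factor 1.75.
- Per-week dose, A/B = 7/3, q = 0.10: 0.518/(0.518 + 2.813) = 0.16, factor 1.09.
- Per-week dose, A/B = 7/3, q = 0.50: 1.44/(1.44 + 1.81) = 0.44, factor 1.34.

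For total dose at q = 0.50, the factor ranges from 1.50 to 2.33 when m/s is varied over 0.6/0.25, 0.5/0.25, 0.6/0.3 and 0.7/0.2, and A/B over 21/3, 21/4 and 27/4.

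**The case for a change.** The best case for a change is that the inconsistency is in current text and reaches a named analysis. Four weeks is the only calendar figure offered for the camp, and the same section makes it optional. Data from up to 71 + 43 + 20 = 134 children will be pooled across sites, so a reader should be able to tell whether delivery was alike. Naming the dose metric and tabulating format by site and arm would cost little. The reading in which home practice and reports continue after a compressed camp is written nowhere and sits poorly with homework set between sessions.

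Most of this stands as a request for clarity. The label does not fit a back-to-back camp, and the passages must be reconciled; which schedule is right is not for this review to say. Tabulating delivery format by site and arm would be sensible reporting.

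What does not stand is the step from unclear wording to a faulty analysis. The schedule sentence reads as a deliberate permission, and the four-week phrase can be read as a label or an outer limit. A weekly form still works for a camp that fits in one week: it yields one report. The text does not say that reports stop at the last session, and the unseen summary of measures and timing may settle the matter. Any figure for false-positive risk in Aim 3 would need an assumed share of back-to-back camps, an assumed direct effect of format and assumed practice habits, so it would describe those assumptions and not this trial.

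**Conclusion.** The inconsistency is real but confined to wording. The four-week description and the back-to-back option must be reconciled with each other and with the weekly report. No analysis needs to change as a result.

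On the consecutive-day reading, the camp spans differ about 6.75- to 9-fold and the reports number about one against three or four. The randomized Aim 1 contrast is unaffected provided format is balanced across arms, and nothing in the documents suggests that it is not. Aim 3 is exploratory, and the two conditions for confounding are not shown to hold. The choice between total and per-week dose is a detail that analysts can settle sensibly from the forms collected, if the uploaded summary has not already done so. A format-adjusted slope is a trade-off with no demonstrated gain: it discards practice variation that is genuine dose and, under the assumed inputs above, widens the standard error 1.09- to 1.75-fold at back-to-back shares of 10% to 50%.

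The conclusion would need another look if camp records showed that both formats were used and were unevenly spread across the arms.

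### ICPS rests on the phase locking value, which rises as trials get fewer; on unmatched error trials, a larger error fall under Structured Games would inflate the ICPS contrast

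*Combined protocol and SAP*

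**What the plan says.** The ICPS paragraph of section 6 (Research Design and Methods) gives the index: "Functional connectivity will be assessed using interchannel phase synchrony (ICPS), based on the phase locking value (PLV), derived from the RID TFDs". It fixes the theta band, the ERN time window and the electrode pairs (FCz with lateral frontal sites). It does not say which trials enter, how many are needed, or whether counts are matched. For the rest it relies on an approach that the document does not show: "Using the same approach previously employed by our group".

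Three other places bear on which trials are used and how many there are:

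- Section 5 describes the construct: "The ICPS reflects the transmission of this error signal to the dorsolateral prefrontal cortex in order to implement the specified control".
- The Zoo task description in section 6 sets the trial supply: "The task includes 8 blocks, each containing 30 unique animals (Go trials) and 10 orangutans (No-Go trials) in random order".
- The ERN paragraph in section 6 says of error and correct responses: "Differentiation between these trial types is the primary ERN measure". No matching sentence exists for ICPS.

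The only related safeguard is also in the ERN paragraph: "The number of NoGo errors and response times (RTs) to Go trials will also be considered in NP analyses, as performance can affect ERN amplitude".

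Section 5 names ERN and ICPS as the neural markers of effortful control (EC). The opening of section 6 puts such markers in the primary comparison: "Primary analyses will test for group mean differences in neurophysiological and behavioral indices of EC". Aim 1 in section 4 gives the direction: "We hypothesize that Kidpower-Structured Games will produce greater increases in neurophysiological and behavioral markers of EC".

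**The concern.** PLV is the length of the average of n unit vectors, one per trial. With few trials that average is long partly by chance, so PLV is biased upward, and more so as n falls. The Zoo task is itself a test of EC. If Structured Games works, children in that arm may make fewer No-Go errors after training, leaving fewer error trials at the second visit. PLV computed on those trials would then rise with no change in synchrony, in the direction that Aim 1 predicts.

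What is at stake is attribution. A fall in errors would be a real behavioural change, but it could be read as stronger coupling between medial and lateral frontal sites, which is the target-engagement claim of Aim 1 for this index.

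**Working it through.** The plan gives no error count, PLV value, SD, alpha or power figure, so there is no stated result to reproduce.

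**Inputs from the documents.** No-Go trials per visit: 8 × 10 = 80, the ceiling on commission errors. Go trials: 8 × 30 = 240. Pooled sample: 71 + 43 + at most 20 = 134, or 67 per arm if allocation is 1:1 and nobody is lost.

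**Assumptions.** True PLV (R) 0.2 to 0.5; between-child SD of R 0.08 and visit SD 0.05; von Mises phases; Poisson error counts with log-normal child variation (SD 0.3), limited to 6–80; two-sided 5% t-test on pre-to-post change; PLV taken across trials.

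**Size of the bias.** For n independent trials,

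E[PLV²] = R² + (1 − R²)/n.

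At R = 0.3:

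- n = 24: 0.09 + 0.91/24 = 0.128
- n = 18: 0.09 + 0.91/18 = 0.141
- n = 12: 0.09 + 0.91/12 = 0.166

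Simulated mean PLV at the same true 0.3 is 0.337 (n = 24), 0.347 (18), 0.376 (12) and 0.304 (200).

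**False-positive rate, raw error-trial PLV, no true change, 67 per arm** (2,000 replicates per cell, Monte Carlo SE 0.5–1.1 points):

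| Errors, Structured Games | Errors, Child-led Play | R = 0.2 | 0.3 | 0.4 | 0.5 |
|---|---|---|---|---|---|
| 24→18 | 24→24 | 11% | 8% | 6% | 6% |
| 24→16 | 24→20 | 8% | 8% | 6% | 6% |
| 40→28 | 40→40 | 11% | 8% | 5% | 6% |
| 24→12 | 24→18 | 20% | 13% | 10% | 7% |
| 24→12 | 24→24 | 44% | 25% | 16% | 10% |
| 24→16 | 24→16 | 5% | 5% | 6% | 5% |

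Repeat runs of the moderate cells (first three rows) reach 12%. In the fifth row the spurious difference in PLV change is 0.059, 0.045, 0.034 and 0.023. At 50 per arm the first row becomes 5%–9% and the fifth 10%–33%.

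**Which trials enter matters.** Error-minus-correct PLV keeps the bias, because about 200 correct Go responses carry almost none of it: 5%–10% for 24→18 and 10%–37% for 24→12, each against no change. PLV on correct trials only, or on all responses pooled, gives 4%–6%.

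**An unbiased index.** Pairwise phase consistency is PPC = (n·PLV² − 1)/(n − 1). Substituting the expectation gives (nR² + 1 − R² − 1)/(n − 1) = R², whatever n is. In every scenario above, PPC and PLV with counts matched within child both give 4%–6%.

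**Error count as a covariate.** Adjusting for change in error count gives 5%–9% (linear) or 4%–6% (in 1/n), so it removes most of the artefact. It also conditions on something training may change. Suppose one EC gain drives both a true PLV rise of 0.10 and errors 24→18. Power at R = 0.2/0.3/0.5 is then 41%/44%/63% with the linear covariate, 47%/56%/77% with matching and 55%/64%/85% with PPC.

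**The case against.** The strongest reply is that the plan refers to an established pipeline, and trial type, matching and minimum counts may all be defined there. The section is limited to one page, so missing EEG detail does not show that matching is absent. This stands. It is why the point is conditional and why a sentence confirming that counts are matched would close it.

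Second, the section 5 wording about an error signal describes a construct, not the set of trials averaged. This also stands. Error trials are the natural reading, given that wording and the ERN window, but a reader who takes it as stated goes further than the documents do.

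Third, no passage predicts a larger fall in No-Go errors under Structured Games. Child-led Play is presented as an active condition with cognitive benefit, and both arms repeat the task, so some fall in both is plausible and equal falls cancel. This weakens the largest figures, which need no change at all in the comparator.

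Fourth, the plan already promises to consider error counts in neurophysiological analyses, which may well include ICPS. That is partly an answer. But the reason given concerns ERN amplitude, no method is stated, and the covariate reading can remove real effect. A sensitivity analysis would be unobjectionable, but would leave the primary index biased.

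Fifth, the realistic effect is small: for 24→18 against no change, the spurious difference is about 0.02 at R = 0.2 and 0.01 at R = 0.5. This stands too. The 44% cell also depends on the assumed visit SD; at 0.10 to 0.15 it drops to roughly a third.

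**Conclusion.** The concern holds conditionally. PLV is the stated index, it is biased upward when trials are few, and the bias favours the hypothesis if all three conditions hold: error-trial PLV (alone or minus correct), no equalising of counts in the earlier pipeline, and a larger error fall under Structured Games. False-positive rates are then about 5%–12% for moderate differential falls, 7%–20% for 24→12 against 24→18, and 10%–44% only when errors halve in one arm with no change in the other. They are nominal when falls are equal. All of these rest on assumed counts, synchrony and SDs, and 67 per arm is a ceiling. True PLV below 0.2 would make the bias larger.

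Three stronger readings should be resisted. The 44% is an extreme cell, not the expected error rate of this trial. The documents do not show that the ICPS result will be spurious, since none of the three conditions is stated. Nor does the point extend to Aim 2: among 67 children with no true relation, rejection is 5%–6% when error change and anxiety change are uncorrelated, 5%–8% at a correlation of 0.3 and 5%–12% at 0.5.

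This is a low-cost improvement to one neural index among several primary measures.

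**What to change.** 1. Make the primary ICPS index unbiased in trial count. Pairwise phase consistency is preferable, computed at each time-frequency point and channel pair before averaging, with negative values kept. Report raw PLV as a sensitivity analysis. PLV with counts matched within child across the two visits is an acceptable alternative. If the existing pipeline already matches counts, saying so is enough.
2. State which trial types enter ICPS and that synchrony is computed across trials, before arms are compared.
3. Tabulate No-Go errors by arm and visit.
4. Keep the primary contrast unadjusted for post-training error count. Use error count and response time only in sensitivity or mediation analyses.
5. Do not exclude children from the primary analysis for few post-training errors beyond the technical minimum needed to compute the index, since that could drop those who improved most. Report any such losses by arm.

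The cost is one formula or one subsampling step plus a few sentences, with no new data. The main downside is less direct comparability with earlier PLV results. For a true PLV rise of 0.10 with 24 errors at each visit and 67 per arm, power at true PLV 0.2/0.3/0.5 is 60%/73%/87% with raw PLV, 59%/73%/90% with pairwise phase consistency and 55%/68%/83% with matching. Where errors fall, matching loses more, as the shared-gain figures above show.
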